2.5 PRECLINICAL STUDIES OF CELL THERAPIES IN ASD

Mouse models of single gene disorders that are associated with the ASD phenotype, such as Fragile X syndrome, Rett syndrome, and Tuberous Sclerosis Complex syndrome, have been used to study the effects of cellular therapy, such as MSCs, on both brain and behavior. Reported data from such animal studies may reflect differences related to the specific genetic subtype of ASD and may not generalize to all cases (e.g. idiopathic ASD).

Derecki et al⁸⁵ report recovery of function in a mouse model of Rett syndrome, an X-linked condition associated with ASD typically caused by a mutation of the *MECP2* gene. This gene encodes a methyl-CpG-binding protein, and the mutation leads to deficient phagocytic function in glial cells. Transplantation of cells from wild type bone marrow via intravenous infusion arrested disease development in the mouse model of Rett syndrome (*Mecp2*-null C57BL/6 mice). Following engraftment, survival was improved, breathing patterns normalized, apneas were reduced, body weight increased, and locomotor activity was improved.

The BTBR T^* *Itpr3^{tf}I* (BTBR) mouse strain, derived from the inbred Black and Tan BRachyury strain, is another mouse model of ASD. In addition to impaired social behavior, aberrant communication, increased repetitive behaviors, and increased cognitive rigidity, BTBR mice also exhibit increased levels of peripheral CD4+ T-cells, peripheral B-cells, and serum and brain

immunoglobulin levels, among other immune abnormalities.⁸⁶ Segal-Gavish, et al⁸⁷ delivered human MSCs to BTBR mice via intraventricular injection into the central nervous system. Mice were immunosuppressed with cyclosporine before and after treatment. In this model, improvements in all three domains – social behavior, stereotyped behaviors, and cognitive rigidity – were observed in MSC-treated mice compared to controls. Differences in anxiety-related behaviors and locomotion were not observed.

These mouse models demonstrate the potential for benefit from cellular therapies in at least certain subtypes of ASD.

2.6 OUTCOMES OF CELL THERAPIES IN CHILDREN WITH ASD

The autism and cellular therapies teams at Duke have partnered to test whether intravenous infusions of autologous or allogeneic cord blood or allogeneic cord tissue derived MSCs would be safe, feasible and improve core symptoms of autism in affected individuals. Results of these studies are summarized below.

DukeABCs Clinical Trial: Duke investigators recently completed and published the results of an open-label Phase 1 safety and tolerability study in 25 children (ages 2-5 mean age 4.5 years), diagnosed with ASD who were treated with a single intravenous infusion of **autologous** CB and followed for a year (ClinicalTrials.gov ID: NCT02176317).⁸⁸ CB was administered as a single infusion (median infused dose: 2.6x10⁷/kg, range: 1.0x10⁷/kg to 8.1x10⁷/kg). No immunosuppression was administered prior to infusion.

The safety and tolerability profile of autologous CB infusion in ASD was excellent. No serious adverse events were reported, and adverse events, in general, were sparse. Three children had mild allergic reactions associated temporally with the infusions, consisting of cough and hives during infusion for 1 child and cough post-infusion for 2 children. Also, one child was noted to be more irritable for 2 days post-infusion. No participants discontinued prematurely from the study due to adverse events.

With regard to preliminary assessments of efficacy, improvements in social communication abilities were noted on the caregiver-completed Vineland Adaptive Behavior Scales-Second Edition (VABS-II) and on the Pervasive Developmental Disorder Behavior Inventory (PDDBI) (figure 4). The Clinical Global Impression-Improvement scale, completed by clinicians, reflected beneficial changes during the 6-month period post-infusion in core ASD symptoms in approximately 60% of the participants, as manifested by the participants' increased social communication skills, receptive/expressive language, decreased repetitive behavior, and decreased sensory sensitivities. In computerized eye-tracking assessments, the participants manifested improvements in social attention. Participants, on average, showed a 20% increase in odds of gazing at the actress' eyes over time (OR=1.20, 95% CI: 1.00, 1.43, p5.048). A 7-point change in VABS-II socialization standard score was associated with a 14% increase in odds of gazing at the actress (OR=1.14, 95% CI: 1.07, 1.21; p<.001).⁸⁸

Electrophysiological recordings were taken during viewing of dynamic social and nonsocial stimuli at 6 and 12 months post-treatment. Significant changes in EEG spectral characteristics were found by 12 months post-infusion, which were characterized by normalization of the EEG spectrum, reflected in increased alpha and beta power and decreased EEG theta power.⁸⁹

Figure 4: Changes in ASD Symptoms after Autologous CB Infusion. Panel A: Vineland-II socialization domain standard scores at baseline and six months after infusion (p=0.02 baseline to six months). Panel B: Distribution of Vineland-II socialization domain standard scores stratified by nonverbal IQ. Panel C: Vineland-II communication domain standard scores at baseline and six months after infusion (p<0.01 baseline to six months). Panel D: Distribution of CGI-I scores at six (blue) and 12 (red) months post-infusion. Sample sizes are N=25 for baseline and 6-month time points and N=22 at 12-months.

Time Point	Median	Mean	SD
Baseline	76.00	75.48	20.32
6 Months	86.00	81.38	22.75
12 Months	86.00	80.25	23.34

Vineland Communication Domain

)

)

)

)

There was also some evidence that improvements in social behavior were found to be associated with increases in connectivity across brain regions when assessed via diffusion tensor imaging (obtained via MRI scans). In an open label trial evaluating the efficacy of autologous cord blood for treating autism symptoms, improvement on 3 behavioral outcome measures was correlated with increased connectivity between the left temporal pole and the left hippocampus (VABS II p<0.001; Expressive One Word Picture Vocabulary Test-Fourth Edition (EOWPVT-4) p<0.05; CGI-I p<0.0001). Improvement on both the VABS-II and the EOWPVT-4 was correlated with increased connectivity between the fusiform and putamen (VABS II p<0.05; EOWPVT-4 p=0.01) as well as between the inferior temporal gyrus and the hippocampus (both p<0.05), both in the left hemisphere. Finally, there was a significant correlation between improvement on both the VABS-II and the CGI-I and increased connectivity between the inferior temporal gyrus and superior temporal gyrus (VABS-II p<0.05, CGI-I p<0.01) and between the temporal pole and globus pallidus (VABS II p<0.01; CGI-I p<0.05) in the left hemisphere. Improvement on the VABS II and CGI-I was also significantly correlated with increased connectivity between the frontal pole and globus pallidus and the insula and putamen in the right hemisphere (all p<0.05). Based on these data, a Phase 2 randomized study was conducted to evaluate the efficacy of CB therapy versus placebo in children with ASD. Data analysis of this trial is currently in progress.

MSCs in ASD: One Chinese study enrolled 37 children with ASD and treated them with 4 doses of either umbilical cord blood mononuclear cells (CBMNC, given both intravenously and intrathecally) (n=14), CBMNC + intrathecal umbilical cord-derived mesenchymal stem cells (UCMSC) (n=9), or standard therapy (n=14).³⁴ The only treatment-related side effect was transient fever in five patients. At six months post-treatment, both treated groups demonstrated greater improvement in multiple ASD measures (Childhood Autism Rating Scale, Clinical Global Impression scale, Aberrant Behavior Checklist) than the placebo group, indicating a potential therapeutic response.

A total of 66 non-serious Adverse Events (AEs) that were not specifically attributed to the study product were reported among 11 of the 12 enrolled participants (Figure 6). All of these reported events were Mild. The most frequently occurring event, agitation during the infusion procedure, was associated with the requirements of placing and maintaining an IV and being confined to a hospital room for the infusion, and all of these events resolved on the same day. A total of 22 other psychiatric or behavioral symptoms were reported in 7 different participants: 2 participants/2 events in Cohort 1, 1 participant/5 events in Cohort 2, and 4 participants/15 events in Cohort 3. These symptoms included aggression (n=2), agitation (n=5), anxiety (n=3), defiant behavior (n=2), depression (n=1), emotional labiality (n=1), insomnia (n=3), intentional self-injury (n=1), and stereotopies (n=4). Of note, 3 participants accounted for 17/22 of the psychiatric or behavioral adverse events. Aside from agitation during the infusion procedure, there was a trend of increasing frequency of non-serious adverse events with increasing number of doses administered, but this was not statistically significant. There were no differences observed in the frequency of AEs according to lot number (GMP-075: median=9 events/participant, range: 1-12; GMP-087: median=4.5, range: 0-13; GMP-088: median=3.5, range: 3-50) (P_{Kruskal-Wallis}=0.58). There were no concerning changes in blood counts, chemistries, basic inflammatory markers (CRP, ESR), or humoral and cellular immune profiles throughout the study. All participants remained Coombs negative.

Six months after the initial hCT-MSC dose, development of anti-HLA class I antibodies was observed in 5 of 9 participants who did not have detectable HLA antibodies pre-treatment. HLA antibody data is available on all 12 participants at baseline and 6 months, and 11/12 participants at ≥12 months after their final hCT-MSC dose. In those participants who developed new HLA antibodies by six months, the HLA antibodies persisted at ≥12 months (figure 7). The HLA antibodies were directed against HLA alleles/antigens expressed on the MSCs and not by the patient. There were no associated clinical events in patients who developed anti-HLA antibodies.

DQ=Developmental Quotient, VABS=Vineland Adaptive Behavior Scales-Third Edition (VABS-3) Socialization Standard Score, PDDBI=Pervasive Developmental Disorder Behavior Inventory Autism Composite, CGI=Clinical Global Impression-Improvement scale

*Clinically significant improvement = 3 points.

2.7 STUDY RATIONALE AND HYPOTHESIS

The mechanistic rationale and overarching theory of this line of investigation is that hCT-MSC can act through paracrine and trophic mechanisms to favorably modulate ongoing inflammation and/or immune pathology in the brain, suppress microglial activation, and possibly protect neurons from further damage. The primary hypothesis of this phase I clinical trial is that administration of hCT-MSCs will be safe and tolerable and result in improvement in the social communication abilities, as measured via objective ratings of social communication abilities during caregiver-child interaction.

In many contexts, MSCs suppress, rather than augment, immunological and inflammatory responses. Documented mechanisms include shifts in effector T cells such as generation of regulatory T cell populations and changes in monocyte/dendritic cell cytokine generation leading to anti-inflammatory cytokines. Therefore, it is plausible to consider a population of MSCs as an immunological and/or anti-inflammatory agent. Both postmortem brain tissue studies and PET imaging data from living individuals with ASD have revealed evidence of increased microglial activation, suggesting that immune and/or inflammatory mediated brain damage plays a role in the etiology of ASD as discussed above.⁹⁰ Thus, hCT-MSC may be a candidate therapy for ASD because of the immunomodulatory activities of MSCs.

2.8 STUDY DESIGN

This is a single site, prospective study of one intravenous infusion of human umbilical cord tissuederived mesenchymal stromal cells (hCT-MSC) in toddlers with autism spectrum disorder (ASD). Toddlers 18 months to <4 years (3 years 364 days) of age with a confirmed diagnosis of ASD will be eligible to participate. Diagnosis will be confirmed at the time of the eligibility visit at the Duke Center for Autism and Brain Development. All participants will receive a single intravenous dose of 2x10⁶/kg hCT-MSC per kilogram at baseline. Assessments will be conducted at baseline and 6 months, with remote follow-up assessments at 12 months.

The primary purpose of this study is to evaluate safety and feasibility. Safety assessments include monitoring of acute infusion reactions, adverse events, incidence of infections, and markers of alloimmunization. Clinical outcome measures will also be described. A key clinical outcome measure is the change in social communication abilities from baseline to 6 months based on the Joint Engagement Rating Inventory (JERI), a commonly-used and well-validated coding system for rating the quality and quantity of social communication skills in toddlers with and without ASD.⁹¹ JERI coding rates social communication abilities on a 1 to 7 scale and factors in both the quantity and quality of skills. The total joint engagement score as well as ratings on all JERI subscales that comprise the total score will be described.

Other clinical endpoints will include the PDD Behavior Inventory (PDDBI) autism composite score, the mean of the Socialization Subscale Standard Score and Communication Subscale Standard Score on the Vineland Adaptive Behavior Scales (VABS-3), the Clinical Global Impression Scale (CGI) – Severity and Improvement Scales, the Communicative Development Inventories (CDI-2): Words & Sentences subscales, and the Pediatric Quality of Life Scale (PedsQL Generic Core Scale).

Exploratory clinical endpoints will include autism symptoms measured by an app that elicits and records autism symptoms on an iPad (SenseToKnow), PDD Behavior Inventory (PDDBI) Subscales, and VABS-3 Standard Score and age equivalent for the following subscales: Socialization, Communication, and Daily Living and the Standard Score and age equivalent for the VABS-3 Adaptive Behavior Composite.

Safety and VABS-3 assessments will also be conducted remotely at three and 12 months. Duration of study participation will be 12 months from the time of the baseline infusion.

2.9 RISKS AND BENEFITS

Potential risks associated with infusion of MSCs include a reaction to the product (rash, shortness of breath, coughing, wheezing, difficulty breathing, hypotension, hypertension, hypoxia, swelling around the mouth, throat or eyes, tachycardia, bradycardia, diaphoresis), transmission of infection, and HLA sensitization. Theoretical risks that must be considered but have not been associated with MSC administration in humans include the possibility of immune suppression and ectopic tissue formation. Cord blood collected with the cord tissue used to manufacture hCT-MSC is screened for infection, and the product must meet release criteria prior to infusion, as described below. Participants will not receive immunosuppressive therapy prior to or after infusion of hCT-MSC cells. Additionally, an inherent risk in completing study procedures in person is possible exposure to COVID-19; however, social distancing, screening, masking, cleaning and other safety procedures in line with the most recent guidelines from Duke Health and the Duke University School of Medicine have been implemented to minimize this risk as much as is feasible.

Potential benefits of this intervention include the possibility that hCT-MSC may, via direct or indirect mechanisms, induce changes that result in the reduction of the participant's core ASD symptomatology and improvement in abilities affected by ASD symptoms.

3.0 STUDY OBJECTIVES

- 1. To determine the safety and tolerability of a single intravenous infusion of hCT-MSC in very young children with ASD.
- 2. To determine whether there are improvements in social communication abilities during caregiver-child interaction from baseline to six months following an infusion at baseline.

4.0 STUDY DESIGN

4.1 GENERAL DESIGN

This is a single site, phase I, open-label, prospective study of one intravenous infusion of human umbilical cord tissue-derived mesenchymal stromal cells (hCT-MSC) in 12 toddlers \geq 18 months to <4 years (3 years 364 days) of age with autism spectrum disorder (ASD). All participants will receive a single intravenous dose of 2x10⁶ hCT-MSC per kilogram at baseline. The primary outcome is safety, as measured by the incidences of infusion reactions, infections, and new-onset clinically significant anti-HLA antibodies. The main clinical outcome measure is the change in social communication abilities from baseline to 6 months based on the Joint Engagement Rating Inventory (JERI).⁹¹ Duration of study will be 12 months from the time of the initial infusion.

4.2 STUDY FLOW CHART

4.3 STUDY ENDPOINTS

Safety Endpoints:

Safety of hCT-MSC infusion in children with ASD will be assessed by:

- 1. Incidence and severity of infusion reactions
- 2. Incidence and severity of product-related infections
- 3. Evidence of alloimmunization via anti-HLA antibodies
- 4. Incidence and severity of graft vs. host disease
- 5. Incidence and severity of unexpected adverse events, by relation to study product

Efficacy Endpoints:

The primary clinical outcome measure is the change in social communication abilities from baseline to 6 months based on total score (1-7) on the Joint Engagement Rating Inventory (JERI), a commonly-used and well-validated coding system for rating the quality and quantity of social communication skills in toddlers with and without ASD.⁹¹

Change measured on the following endpoints from baseline to six months will be compared:

- 1. PDD Behavior Inventory Autism Composite Score (PDDBI)
- 2. Mean of the Socialization Subscale and Communication Subscale standard scores on the Vineland Adaptive Behavior Scales (VABS-3)
- 3. Clinical Global Impression Scale (CGI) Severity and Improvement (Improvement at 6 months only

4. Communicative Development Inventories (CDI-2): Words & Sentences subscales

Exploratory Endpoints:

Change measured from baseline to six months will be evaluated on the following outcome measures.

- 1. Changes in auditory orienting, facial expressions, look duration, attention to social and nonsocial stimuli, postural sway, and vocalizations as measured via computer vision analysis by an app that elicits and records autism symptoms on an iPad (SenseToKnow)
- 2. PDD Behavior Inventory (PDDBI) Subscales
- 3. VABS-3 Socialization Subscale Standard Score and age equivalent
- 4. VABS-3 Communication Subscale Standard Score and age equivalent
- 5. VABS-3 Daily Living Subscale Standard Score and age equivalent
- 6. VABS-3 Adaptive Behavior Composite Standard Score and age equivalent
- 7. Pediatric Quality of Life Scale Generic Core

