8.4 SAMPLE SIZE AND POWER CALCULATIONS

The proposed trial is an open label Phase I trial of one intravenous infusion of hCT-MSC in toddlers 18 months to <4 years (3 years 364 days) of age with a diagnosis of ASD. The primary outcome is safety, as measured by the incidences of infusion reactions, infections, and new-onset clinically significant anti-HLA antibodies. Efficacy measures will also be assessed. The primary efficacy measure is coded time spent in sustained engagement with the caregiver in a brief semi-structured parent child interaction task (PCIT). The change on this outcome measure from Baseline to Month 6 will be analyzed.

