9.2 ADVERSE EVENT REPORTING

All adverse events reported or observed during the study beginning at the time of the initial infusion must be recorded. AEs occurring in 5% of enrolled participants will be reported in clinicaltrials.gov. Information to be reported includes date when the site became aware of the event, investigator-specified assessment of severity and relationship to study therapy, whether there is an alternative etiology, seriousness, as well as any required treatment or evaluations, and

outcome. In general, investigators should report adverse events as diseases or syndromes whenever possible, instead of reporting individual component symptoms, signs, laboratory abnormalities, and sequelae.

Severe adverse infusion reactions (fatal, life-threatening or requiring hospitalization) will be reported within seven calendar days of receipt of the information. All fatal or life threatening SAEs will be reported by the investigator or its representatives to the FDA by telephone or fax within seven calendar days after receipt of the information, following FDA guidelines. All serious and unexpected AEs will be reported to the FDA via a written report within 15 days of receipt of the information (21 CFR 312.32). If the principal investigator assesses an event to be unrelated to the study, then the event will not require expedited reporting but will be included in the annual summary report.

The following events within 24 hours of hCT-MSC infusion will also be recorded in the e-CRF: infusion reaction, sinus bradycardia, sinus tachycardia, hypertension, hypotension, fever, rigors/chills, nausea, vomiting, infection, dyspnea, hypoxia, and hemoglobinuria.

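### Safety endpoint 5 in section 4.3 counts only unexpected adverse events, a term the plan leaves undefined, although every adverse event is recorded

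*Combined protocol and SAP*

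**What the plan says.** Section 4.3 lists five safety endpoints. Four name specific risks: "Incidence and severity of infusion reactions", infections related to the product, alloimmunization, and graft-versus-host disease. The fifth is the only one for adverse events in general, and it reads "Incidence and severity of unexpected adverse events, by relation to study product".

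Other sections are wider. Objective 1 in section 3.0 is safety and tolerability. Section 2.8 uses no qualifier: "Safety assessments include monitoring of acute infusion reactions, adverse events, incidence of infections, and markers of alloimmunization". Section 9.2 requires that "All adverse events reported or observed during the study beginning at the time of the initial infusion must be recorded", with severity and relationship among the items to be reported for each event.

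The statistical section does not close the gap. Section 8.4 states "The primary outcome is safety, as measured by the incidences of infusion reactions, infections, and new-onset clinically significant anti-HLA antibodies", section 8.5 repeats those three, and section 8 contains no general adverse-event summary.

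**The concern.** Expectedness is normally a test for how fast an event must be reported. Apart from a loose use in the title of section 7.4, that is its role elsewhere in this protocol: the 15-day report in section 9.2 and the handling of serious events in sections 9.3 and 10.0. It does not measure tolerability. As a filter on an endpoint, it makes the reported count depend on a label, and section 9.1 gives no rule for assigning that label.

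In an open-label, single-arm study of 12 children, the label could be assigned after the event is known. The events at stake are those outside the four named risks, for example behavioural ones. Section 2.6 reports of the earlier hCT-MSC study that "A total of 22 other psychiatric or behavioral symptoms were reported in 7 different participants", in addition to agitation during the infusion procedure. The follow-up questionnaire in Appendix 1 asks about the same kinds of event (sleep, aggression, agitation, self-harm, mood). The trial therefore collects them, but guarantees them no place in its severity-by-relation summary.

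**Working it through.** There is no sample-size or power figure to reproduce, because section 8.4 gives none. The check compares the sections and then sizes what could be left out.

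**1. Coverage, side by side.**
- Section 3.0, objective 1: safety and tolerability, no filter.
- Section 2.8: adverse events, no filter.
- Section 9.2: all adverse events recorded, with severity and relationship.
- Section 4.3, items 1 to 4: named risks, no expectedness filter.
- Section 4.3, item 5: adverse events, unexpected only.
- Section 8.5: infusion reactions, infections and anti-HLA antibodies; no general summary.

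An event outside items 1 to 4 therefore enters a section 4.3 endpoint only if it is classed as unexpected. (Section 8.5 would also pick up infections not related to the product.)

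**2. The earlier study's count (section 2.6).**
- By symptom: 2 + 5 + 3 + 2 + 1 + 1 + 3 + 1 + 4 = 22 events.
- By cohort: 2 + 5 + 15 = 22 events, in 2 + 1 + 4 = 7 participants.

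The stated figures reproduce.

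**3. Proportions affected.** Exact (Clopper-Pearson) 95% limits are the 0.025 quantile of Beta(x, n − x + 1) and the 0.975 quantile of Beta(x + 1, n − x), with n = 12.
- Any of the 66 non-serious events: x = 11, 11/12 = 91.7%, limits 61.5% to 99.8%.
- Behavioural event other than procedural agitation: x = 7, 7/12 = 58.3%, limits 27.7% to 84.8%.

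**4. Share that could leave item 5 if the same experience recurred.**
- If only the 22 behavioural events were classed as expected: 22/66 = 33%.
- If procedural agitation were too: section 2.6 calls it the most frequent event but gives no count k. Assume k is at least 6 (just above the largest listed count, 5) and at most 66 − 22 = 44. The share is then (22 + 6)/66 = 42% up to (22 + 44)/66 = 100%.
- If none were classed as expected: 0%.

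The denominator of 66 is taken as printed.

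**5. What the registry rule catches.** Section 9.2 says "AEs occurring in 5% of enrolled participants will be reported in clinicaltrials.gov". Here 0.05 × 12 = 0.6 of a child, and one child is 1/12 = 8.3%. Read as 5% or more, the rule lists every event type seen in at least one child.

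**6. Direction.** A filter can only remove events. Relative to a summary of all adverse events, item 5 gives the same count or a smaller one, never a larger one.

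**The case against.** The strongest reply is that item 5 is meant as a catch-all. Items 1 to 4 are the anticipated risks, and *unexpected* may simply mean everything else. The protocol does use the word loosely: section 7.4, on care during unexpected events, includes cough, wheezing and difficulty breathing, which section 2.9 lists as potential risks. That reading is plausible, but the text does not establish it. If it is what was intended, the rewording proposed here states it outright.

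Several stronger inferences are tempting, and the documents do not support them:

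- *That the earlier study made behavioural events expected.* No section says so. Section 2.9 lists no behavioural risk, and the earlier events were all mild and not specifically attributed to the product. They could equally be classed as unexpected and counted.
- *That infusion-day events in general are excluded.* Item 1 counts infusion reactions whatever their expectedness, and section 9.2 adds 13 event types: "The following events within 24 hours of hCT-MSC infusion will also be recorded in the e-CRF". Only non-reaction events, such as procedural agitation, could fall outside both items.
- *That comparison with the earlier study is prevented.* It is not, because every event is recorded with severity and relationship.
- *That 58% forecasts this trial.* It pools three cohorts with 2, 5 and 15 events, 3 children account for 17 of the 22, and this trial gives a single infusion.

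Other safeguards also stand. The stopping guidelines in section 9.5 apply no expectedness test, and the data safety monitoring board receives an annual safety assessment. These protect participants and disclosure. They do not determine what the trial's own endpoint summarizes.

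**Conclusion.** The point holds as a defect of endpoint wording. The only general adverse-event endpoint carries a filter that the available text does not define. That filter is narrower than objective 1, section 2.8 and section 9.2, and nothing in section 8.5 makes up for it.

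Its size cannot be estimated, only bounded. On the earlier study's experience, the share of events left out could be nil, 33% if the 22 behavioural events were classed as expected, or 42% to 100% if procedural agitation were as well. The last range rests on the assumed k, and all of these shares rest on the printed total of 66. The direction is fixed: any effect lowers the reported burden. Whether a lowering would actually occur is not shown.

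The primary safety outcome in sections 4.1, 8.4 and 8.5 is unaffected, recording is complete, and the registry listing would be nearly so. The change should still be made, because the plan contradicts its own scope and the correction needs no new data.

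**What to change.** - In section 4.3, item 5, replace the word *unexpected* with *all* and leave the rest of the item unchanged. Show serious events and unexpected events as subsets, and state how expectedness is decided for the latter.
- In section 8.5, add the matching descriptive summary: number of events and number of children affected, by severity and by relation to product.
- Keep expectedness as a criterion for regulatory reporting in sections 9.2 and 9.3.

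The cost is a small edit to two sections and one additional summary table. Severity and relationship are already collected under section 9.2, so no new data, visits or participants are needed.
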